6.9. Prior Medication and Concomitant Therapy

Medications will be classified into anatomical therapeutic chemical (ATC) drug classes using the latest version of the WHO drug dictionary. Medication start and stop dates will be compared to the date of the first dose of treatment to allow medications to be classified as concomitant.

Prior medications are those medications that start and stop prior to the date of the first dose of study treatment. *Concomitant medications* are those medications that start before, on, or after the first day of study treatment and continue into the treatment and assessment period.

For all summary tables of concomitant medications, Preferred Terms of concomitant medication will be sorted by descending frequency in the LY total arm.

Table PYAH.6.6. Summary Tables Related to Concomitant Medications

Analysis	Details
Prior medications	Number and percentage of participants using Preferred Terms of prior medication
	Ordered by decreasing frequency
	No inferential statistics
Concomitant	Number and percentage of participants using Preferred Terms of concomitant medication
medications	Ordered by decreasing frequency
	No inferential statistics

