6.13. Subgroup Analyses

This study is not powered for subgroup analyses; therefore, all subgroup analyses will be treated as exploratory.

Subgroup analyses will be conducted for the primary endpoint. Subgroups may include:

- time from symptom onset to study randomization
- baseline severity of COVID-19
- age group (<35, \ge 35 to <45, \ge 45 to <55, >55 years old)
- gender (male, female)
- race
- ethnicity
- baseline weight ($<60 \text{ kg}, \ge 60 \text{ to } <100 \text{ kg}, \ge 100 \text{ kg}$)
- baseline body mass index (underweight to normal: <25 kg/m², overweight: ≥25 to <30 kg/m² and obese: ≥30 kg/m²)
- concomitant medication of interest use (yes/no)

Treatment group differences will be evaluated within each category of the subgroup regardless of whether the interaction is statistically significant. If any group within the subgroup is <10% of the total population, only summaries of the efficacy data will be provided; i.e., no inferential testing.

The analysis of additional subgroups and/or subgroup analyses on additional endpoints will not require an amendment to the SAP.

Within each subgroup category the relevant summary measure by treatment, treatment differences (compared to placebo) and 95% CIs will be displayed. Also, p-values using appropriate statistical tests for treatment comparison will be provided. Forest plots may be generated to display the treatment difference and 95% CIs for selected efficacy subgroup analyses.

Baseline severity of COVID-19 will be defined using the following definition.

- Severity will be defined to be Moderate if the participant demonstrates the following at baseline:
 - Symptoms:
 - Shortness of breath (with symptom questionnaire severity score ≥1)

OR

 Symptoms of moderate illness with COVID-19, (any symptom questionnaire score >1, excluding loss of appetite)

AND

- Clinical signs suggestive of moderate illness with COVID-19, such as:
 - Respiration rate ≥20 breaths per minute

OR

- Pulse ≥90 beats per minute.
- Else, severity will be defined to be Mild.

Concomitant therapies of interest include remdesivir, lopinavir/ritonavir, chloroquine, hydroxychloroquine, anticoagulants, dexamethasone, or other investigational interventions. Details of the medications included in this subgroup are provided below in Table PYAH.6.11.

Table PYAH.6.11. Concomitant Medications of Interest Subgroup

Drug name	ATC Code	Who Drug Preferred Term
Remdesivir		REMDESIVIR
Kaletra	J05AR	KALETRA
Lopinavir	J05AR	LOPINAVIR

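### The medication-of-interest subgroup for the primary endpoint is not limited to baseline, so drugs started after dosing can decide who is in it

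*SAP*

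**What the plan says.** SAP Section 6.13 opens its list with "Subgroup analyses will be conducted for the primary endpoint. Subgroups may include" and includes "concomitant medication of interest use (yes/no". Every other entry is fixed before dosing: time from symptom onset to randomisation, baseline severity, age, gender, race, ethnicity, baseline weight and baseline body mass index. The medication entry has no such limit. The drugs are described as follows: "Concomitant therapies of interest include remdesivir, lopinavir/ritonavir, chloroquine, hydroxychloroquine, anticoagulants, dexamethasone, or other investigational interventions". Table PYAH.6.11 names them individually and also lists baricitinib.

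Section 6.9 defines concomitant medications as those that "are those medications that start before, on, or after the first day of study treatment and continue into the treatment and assessment period". It keeps a separate class for earlier use: "Prior medications are those medications that start and stop prior to the date of the first dose of study treatment".

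Table PYAH.6.2 ends the treatment and assessment period at the earliest of discontinuing the period, discontinuing the study, or the first post-treatment follow-up visit. Section 5.1.4 places follow-up assessments at Days 60 and 85.

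For each subgroup category, Section 6.13 asks for treatment differences with 95% confidence intervals and adds: "Also, p-values using appropriate statistical tests for treatment comparison will be provided". It sets one limit: "If any group within the subgroup is <10% of the total population, only summaries of the efficacy data will be provided". It labels all subgroup analyses exploratory. Section 6.1.4 makes Arms 12-14 descriptive only, so the comparisons at issue are those in Arms 1-11.

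**The concern.** A subgroup comparison inherits the protection of randomisation only if membership is settled before treatment can influence it. Here a participant can enter the 'yes' group because of something that happened after dosing. If assigned treatment changes how often the listed drugs are started, users on active treatment and users on placebo are no longer comparable, and the same holds for non-users. A difference between the two categories could then be read as effect modification when there is none. A real effect could also look larger or smaller within a category than it is.

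**Working it through.** **Step 1. Who counts as 'yes'.** Apply Section 6.9 and Table PYAH.6.2 to a participant who takes a listed drug and does not discontinue early:

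| Timing of the listed drug | Class under 6.9 | Subgroup | Could treatment affect it? |
|---|---|---|---|
| Starts and stops before dosing | Prior | No | No |
| Starts before dosing, continues | Concomitant | Yes | Start: no |
| Starts between dosing and Day 7 | Concomitant | Yes | Yes |
| Starts on, say, Day 20 | Concomitant | Yes | Yes, and the Day 7 endpoint is already known |

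The group is mixed. The third and fourth rows are the defect. The first row rules out reading the entry as simple pre-dose use, because pre-dose use that has ended is excluded.

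**Step 2. What this can do to the estimates.** The SAP gives no usage rates and no figure to reproduce. The two calculations below are illustrations.

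*Illustration A: no treatment effect on the endpoint.* All inputs are assumed, and chosen so that the overall rate equals the 19% placebo rate used for planning in Section 5.2. Severe course 30% in both arms. Endpoint 40% in severe and 10% in others, so overall 0.30 × 0.40 + 0.70 × 0.10 = 19%. Placebo medication use 40% in severe and 5% in others.

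- Placebo use: 0.30 × 0.40 + 0.70 × 0.05 = 15.5%.
- Placebo users, endpoint: (0.12 × 0.40 + 0.035 × 0.10) / 0.155 = 33.2%.
- Placebo non-users, endpoint: (0.18 × 0.40 + 0.665 × 0.10) / 0.845 = 16.4%.

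Let active treatment lower medication use in severe participants by a given proportion:

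| Reduction | Active use | Users, active vs placebo | Non-users, active vs placebo |
|---|---|---|---|
| 0% | 15.5% | 33.2% vs 33.2% | 16.4% vs 16.4% |
| 25% | 12.5% | 31.6% vs 33.2% (-1.6 points) | 17.2% vs 16.4% (+0.8) |
| 50% | 9.5% | 28.9% vs 33.2% (-4.3) | 18.0% vs 16.4% (+1.6) |
| 75% | 6.5% | 23.8% vs 33.2% (-9.4) | 18.7% vs 16.4% (+2.3) |

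The true difference is zero in every cell. The 0% row is also what a baseline definition gives, because use is then balanced in expectation.

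*Illustration B: a treatment effect acting wholly through early worsening.* Assumed: worsening 30% placebo, 12% active; endpoint 45% if worsened, 8% if not; medication use 50% if worsened, 3% if not.

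- Overall: 19.1% vs 12.4%, odds ratio 0.60, difference 6.7 points.
- Users: 40.5% vs 33.7%, odds ratio 0.75, difference 6.8 points.
- Non-users: 14.7% vs 10.4%, odds ratio 0.68, difference 4.3 points.

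On the odds ratio scale both categories look weaker than the whole. On the difference scale only the non-users do. The pattern differs again from illustration A.

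**Step 3. Does the 10% rule remove the problem?** In illustration B, use is 17.1% on placebo and 8.6% on active. Pooled at equal allocation that is (17.1 + 8.6) / 2 = 12.9%, so testing proceeds. If use among the worsened is 30% instead of 50%, the figures are 11.1% and 6.2%, pooled 8.7%, and no p-value is produced. The rule looks at a category's share of the population, not at balance between arms. Below 10% the summaries are still shown and carry the same bias.

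**The case against.** The case for leaving the text alone is that the analysis is optional, exploratory and openly unpowered, and that no primary or secondary estimate, alpha allocation or interim rule depends on it. The population has mild to moderate illness and Arms 9-11 are low risk, so use of the listed drugs may fall below 10%, in which case no test is run. Precision would be poor anyway. In illustration B with 100 per arm, there are about 17 users on placebo and 9 on active, and the 95% interval for the users' odds ratio of 0.75 runs from roughly 0.14 to 4.1. All of this stands, and it limits how much the point matters. It does not answer it: the exploratory label concerns power and multiplicity, and a summary without a p-value is still biased.

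A reader might also infer stronger claims that the SAP does not support:

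- That the subgroup consists only of drugs started after dosing. Section 6.9 also counts drugs already in use that continue.
- That the listed drugs are given because a participant has worsened, or that treatment changes their use. The SAP states neither; it only leaves both possible.
- That both categories will understate the effect. The two illustrations give different patterns, and on the difference scale illustration B does not show it.
- That p-values will necessarily be reported. They appear only if each category reaches 10%.

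**Conclusion.** The point holds in limited form. As written, the 'yes' group combines use at dosing with use begun later, including after the endpoint has been read, so membership can be affected by assigned treatment. Within-category differences and confidence intervals in Arms 1-11 can be biased, as can p-values where the 10% condition is met. That conclusion follows from Sections 6.9 and 6.13 and Table PYAH.6.2 and needs no numerical assumption. Direction and size cannot be determined from the SAP: the 1.6 to 9.4 and 0.8 to 2.3 points in illustration A, and the odds ratios in illustration B, rest on assumed inputs and show only that the distortion need not be negligible. The primary analysis and its error control are untouched. This is worth correcting because the correction is small, not because a main conclusion of the trial is at risk.

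**What to change.** In Section 6.13, do one of two things:

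1. Define the subgroup by use of a Table PYAH.6.11 medication at or before the start of infusion. State whether a course that ended before dosing counts (either choice is pre-treatment), and give a rule for drugs started on the day of infusion.
2. Remove the entry from the treatment-comparison subgroups and only tabulate post-dose use of these drugs by arm.

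Either is a short text change. No new data are needed, because Section 6.9 already compares medication start and stop dates with the first-dose date. The cost of the first option is that baseline users may be too few for testing; the existing 10% rule already covers that. The cost of the second is that no treatment effect by medication use is reported.

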6.14. Protocol Violations

Protocol deviations will be identified throughout the study. Important protocol deviations (IPDs) are defined as those deviations from the protocol that would potentially compromise participants' safety, data integrity, or study outcome.

A separate document known as the "PYAH Trial Issues Management Plan" describes the categories and subcategories of IPDs and how the IPDs would be identified.

The number and percentage of participants having IPDs will be summarized within category and subcategory of deviations by dosing regimen.

A by-patient listing of IPDs will be provided.

6.15. Interim Analyses and Data Monitoring

6.15.1. Interim Analyses

The ongoing study may be modified based on planned interim analyses. Based on the observed data at the time of the interim analyses, the study may

- suspend enrollment to any treatment arm (or arms) demonstrating lack of efficacy, and/or
- initiate/expand enrollment to an additional/existing treatment arm (or arms).

The modifications proposed are done so to ensure participants are being exposed to treatment with an acceptable risk-benefit profile during the ongoing trial. Additionally, the potential modifications will provide information to more fully characterize the dose response profile.

Monitoring of unblinded safety data (including AEs, SAEs, and selected laboratory measurements) will occur throughout the study and will be conducted by Assessment Committee (AC) members. The AC will review rolling safety data starting after approximately 150 participants are enrolled and have had an opportunity to reach Day 4 to monitor participant safety. These initial ongoing individual reviews of unblinded safety data will subsequently occur at least every 30 days. This is intended as an individual AC member review and does not require a formal meeting. However, any AC member can ask for a full AC meeting based on the rolling review at any time.

An interim analysis is planned when approximately 75 participants in each arm (Treatment Arms 1-5) reach Day 7. An additional interim analysis may be conducted when at least 50% of participants in Treatment Arm 6 reach Day 7 and also when at least 33% of participants in Treatment Arms 7 and 8 reach Day 7.

The primary outcome may be analyzed first when the data is available, i.e. once all patients in Treatment Arms 1-6 reach Day 7 and/or once all patients in Arms 7 and 8 reach Day 7. Periodic adjustments to the allocation ratio may be made to achieve the planned allocation across Treatment Arms at the conclusion of enrollment. If additional placebo participants are enrolled, then the allocation ratio may change accordingly.

The PYAH study may be stopped early based on an unacceptable safety signal(s).

6.15.2. Data Monitoring Committee/Assessment Committee

The sponsor will form an AC to analyze the interim study data. To minimize any bias introduced into the analysis of the study results, analysis plans will be finalized and approved prior to the interim analyses.

The primary goal of the AC is to review the interim results regarding the continuing safety of study participants and the continuing validity and scientific merit of the study. Information that

may unblind the study during the analyses will not be reported to study sites or the blinded study team until the study has been unblinded. If necessary to inform time critical decisions of additional dose(s) to be studied in the program, in order to more effectively address unmet medical needs, questions with simple (e.g. yes/no) answers may be posed to the AC. These questions will be specified in the AC Charter, and the AC will communicate recommendations to the senior management designee.

Overall committee structure information is in Protocol Section 10.1.5. Details of the AC will be provided in the AC charter. Unblinding details are specified in the unblinding plan section of the SAP or in a separate unblinding plan document.

6.16. Planned Exploratory Analyses

6.16.1. Protocol-Defined Exploratory Endpoint

If appropriate, the evaluation of viral resistance will be conducted as described in a separate bioanalytical analysis plan.

6.16.2. Additional Exploratory Analyses Not Defined in the Protocol

6.16.2.1. SpO₂ AUC

The AUC from Day 1 predose to Day 29 (AUC[0-D29]) will be calculated according to the linear trapezoidal rule using the daily SpO₂ values. If multiple values are collected on a given day, the average will be used. No imputations of missing data will be conducted. No AUC(0-D29) values will be calculated when Day 1 predose and/or Day 29 values are missing, or if there are more than 3 values missing in the profile.

The AUC from Day 1 predose to Day 11 (AUC[0-D11]) will also be calculated according to the linear trapezoidal rule using the mean daily SpO₂ values. No imputations of missing data will be conducted. No AUC(0-D11) values will be calculated when Day 1 predose and/or Day 11 values are missing, or if there are more than 1 value missing in the profile.

The AUC will be summarized and plotted by treatment and listed.

Additionally, SpO₂ AUC data will be statistically analyzed using a linear model. The model will contain treatment as a fixed effect, SpO₂ baseline measurement as a covariate, and oxygen source. The LS means and treatment differences (each active treatment minus placebo) will be calculated and presented with their corresponding 95% CIs. All available data will be used in the analysis.

6.16.2.2. Symptom Questionnaire

See Appendix 1 for further details regarding the symptoms and overall clinical status participant questionnaire.

6.16.2.2.1. Loss of Appetite and Changes in Taste and Smell

Participants will rate the loss of appetite and changes in taste and smell with yes/no responses. Responses at Days 3, 5, 7, 11, 22, and 29 will be summarized by treatment in frequency tables and listed.

6.16.2.2.2. Overall Clinical Status

Participants will complete questions about their overall clinical status. Responses at Days 3, 5, 7, 11, 22, and 29 will be summarized by treatment in frequency tables and listed.

6.16.2.3. NIAID Score

See Appendix 3 for further details regarding the NIAID scoring scale.

6.16.2.3.1. Worst NIAID Score

The lowest daily value from Day 1 through Day 11 for a patient on the NIAID ordinal scale will be summarized by treatment groups. Mean value by treatment group will be plotted over time.

6.16.2.3.2. Clinical Worsening Based on the NIAID Scale

Clinical worsening is defined as the proportion (percentage) of participants with any worsening on the NIAID ordinal scale from baseline to Days 3, 5, 7, 11, 22, and 29.

6.16.2.4. National Early Warning Score (NEWS2)

See Appendix 4 for further details regarding the NEWS2 scoring scale.

6.16.2.4.1. Highest Daily NEWS2 Score

The highest daily value from Day 1 through Day 11 for a patient on the NEWS2 ordinal scale will be summarized by treatment groups. Mean value by treatment group will be plotted over time.

6.16.2.4.2. NEWS2 Consciousness Level

Consciousness level assessed by NEWS2 will be summarized using a logistic regression analysis as described in Section 6.1.4.

6.16.2.5. NIAID/NEWS2 Overall Improvement

Overall improvement on the ordinal scales (NIAID, NEWS2) will be summarized by treatment group from baseline to Days 3, 5, 7, 11, and 29.

6.16.2.6. Time to Hospitalization

Time to Hospitalization is defined (in days) as:

(First study day when hospitalized status is changed to "Yes" – Infusion Date +1)

If a patient has been admitted to the hospital or ICU by completion or early discontinuation of study/study treatment, the patient will be censored at the date of their last visit during the treatment and assessment period.

Time to hospitalization will be evaluated during the study treatment and assessment period only and will be summarized by treatment and listed. Cox proportional hazard model will be used.

Time to hospitalization may be presented graphically.

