6.10.3.1.6. Time to SARS-CoV-2 Clearance

See Section 6.10 for more details on the definition of viral clearance and date of viral clearance.

Time to SARS-CoV-2 clearance is defined (in days) as:

(Date when SARS-CoV-2 clearance status is first changed to "Yes" – Infusion Date + 1)

If a patient has not experienced SARS-CoV-2 clearance by completion or early discontinuation of study/study treatment and assessment period, the patient will be censored at the date of their last visit during the treatment and assessment period.

Time to SARS-CoV-2 clearance will be evaluated during the study treatment and assessment period only, and will be summarized by treatment and listed. Cox proportional hazard model will be used.

Time to SARS-CoV-2 clearance will be presented graphically.

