6.10.3.2.2. Time to Symptom Resolution

Time to symptom resolution is defined (in days) as:

```
(First study day when symptom resolution status is changed to "Yes" – Infusion Date + 1)
```

If a patient has not experienced symptom resolution by completion or early discontinuation of study/study treatment, the patient will be censored at the date of their last visit during the treatment and assessment period. If a patient is hospitalized, the patient will be censored at the date of hospitalization.

Time to symptom resolution will be evaluated during the treatment and assessment period only and will be summarized by treatment and listed. Cox proportional hazard model will be used.

Time to symptom resolution will be presented graphically.

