6.10.3.2.7. Time to Symptom Improvement

Time to symptom improvement is defined (in days) as:

(Date when symptom improvement status is changed to "Yes" – Infusion Date + 1)

If a patient has not experienced symptom improvement by completion or early discontinuation of study/study treatment, the patient will be censored at the date of their last visit during the treatment and assessment period. If a patient is hospitalized, the patient will be censored at the date of hospitalization.

Time to symptom improvement will be evaluated during the study treatment and assessment period only and will be summarized by treatment and listed. In addition, a graphical presentation of the symptom improvement will be provided using a KM plot.

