6.10.3.3. Participant Clinical Status

6.10.3.3.1. COVID-19-Related Hospitalization or Death from Any Cause

Proportion (percentage) of participants who experience any of the following by Day 29 will be analyzed:

- COVID-19-related hospitalization (defined as ≥24 hours of acute care), or
- Death from any cause

The proportion of participants that experience hospitalization or death from any cause by Day 29 will be summarized by treatment in frequency tables and listed.

In addition, the number of participants that experience COVID-19 hospitalization or death from any cause by Day 29 will be analyzed using logistic regression to compare active treatment versus placebo at each dose level. If the number of observed events is less than 5 in any treatment arm an exact test (i.e. Fisher's exact) will be conducted instead of using a logistic regression. Data will not be imputed due to dropouts or missing data.

Proportion (percentage) of participants who experience COVID-19 related hospitalization or death from any cause by Days 22, 60, and 85 will also be analyzed.

The safety population will be utilized to analyze COVID-19-related hospitalization or death from any cause.

Based on the 'Hospitalization Events' eCRF page, a COVID-19-related hospitalization event is defined as an event with:

'Reason for Health Care Visit' of 'Primary Study Condition'

AND

- a 'Health Care Service Type' of:
 - o 'General Ward' or 'ICU'

OR

o 'Emergency Room' with a duration of \ge 24 hours.

6.10.3.3.1.1. Bayesian Modeling for COVID-19-Related Hospitalization or Death From Any Cause

Additionally, a Bayesian sensitivity analysis will be performed. A Bayesian logistic regression model will be fitted to evaluate the success criteria by the Lilly statistics group with the model listed below:

$$r_{ij} \sim Binomial(p_{ij}, 1)$$

$$\log\left(\frac{p_{ij}}{1 - p_{ij}}\right) = \alpha_i$$

Where,

 r_{ij} : is 1 if patient j on treatment i was hospitalized and 0 otherwise α_i : a parameter corresponding to treatment i (with i=1 being the placebo group). and priors:

$$\alpha_1 \sim \pi(\alpha_1)$$

At least 2 priors $(\pi(\alpha_1))$ will be considered for α_1 , a diffuse $N(0,100^2)$ and an informative prior based on available information at the time of analysis.

The safety population will be utilized to analyze COVID-19-related deterioration.

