6.16.2.8. Time to Admission to ICU

Time to ICU is defined (in days) as:

(First study day when ICU status is changed to "Yes" – Infusion Date +1)

If a patient has been admitted to the hospital or ICU by completion or early discontinuation of study/study treatment, the patient will be censored at the date of their last visit during the treatment and assessment period.

Time to ICU will be summarized by treatment group for those patients who are admitted to the ICU.

Time to ICU may be presented graphically.

6.16.2.9. Proportions of Participants Hospitalized, Admitted to the ICU, Requiring Mechanical Ventilation

The proportion of participants hospitalized, admitted to the ICU, requiring mechanical ventilation (oxygen source = "Intubation/Mechanical Ventilation") will be summarized separately by treatment group. These endpoints will be evaluated thru Days 7, 11, 15, 22, and 29.

If an event (hospitalization, ICU, or Mechanical Ventilation) occurs, the participant will be defined as having had the event for all subsequent timepoints evaluated. For example, if a participant experiences a hospitalization on day 8, their hospitalization status would be defined as:

- 'No' for the evaluation of hospitalization thru day 7, and
- 'Yes' for hospitalization thru Days 11, 15, 22, 29.

No imputation will be used as these endpoints are based on running records; i.e., an event is only reported if they are observed.

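### Time to hospitalization and time to ICU censor the patients who were admitted, and the Bayesian check on hospitalization or death does not count deaths

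*SAP*

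**What the plan says.** **Time to hospitalization (SAP 6.16.2.6).** Time runs from infusion to the "First study day when hospitalized status is changed to" yes, so admission is the event. A Cox model is planned. The censoring rule is: "If a patient has been admitted to the hospital or ICU by completion or early discontinuation of study/study treatment, the patient will be censored". Censoring falls on the last visit in the treatment and assessment period.

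**Time to ICU (SAP 6.16.2.8).** The formula is analogous, with ICU status in place of hospitalized status, and the censoring sentence is the same. The planned output is descriptive: "Time to ICU will be summarized by treatment group for those patients who are admitted to the ICU".

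**Other time-to-event rules in the same SAP.**
- 6.10.3.1.6: "If a patient has not experienced SARS-CoV-2 clearance by completion or early discontinuation"
- 6.10.3.2.2: "If a patient has not experienced symptom resolution by completion or early discontinuation"
- 6.10.3.2.7: "If a patient has not experienced symptom improvement by completion or early discontinuation"

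**Bayesian sensitivity model (SAP 6.10.3.3.1.1).** The heading names hospitalization or death from any cause, and the model is presented as a sensitivity analysis of that composite. Its outcome r_ij, however, "is 1 if patient j on treatment i was hospitalized and 0 otherwise". The closing sentence calls the outcome COVID-19-related deterioration, a term the SAP does not define.

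**The concern.** In 6.16.2.6 the event definition and the censoring rule cannot both hold. A patient whose status becomes yes is the event by the formula and a censored observation by the rule, while a patient never admitted has no explicit censoring date. Followed as written, the Cox model has nothing to estimate.

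In 6.16.2.8 the sentence conflicts with the section's own formula and with its summary of admitted patients. Inserting 'not' alone would not repair it. If the rule covered patients not admitted to either the hospital or the ICU, a patient treated on a ward but never in the ICU would still have no censoring rule for time to ICU.

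In 6.10.3.3.1.1 the coded outcome is narrower than the endpoint the model is meant to check. A death without hospitalization counts against treatment in the frequentist composite and as a non-event in the sensitivity analysis. Any disagreement between the two could then come from the outcome definition and not from the modelling assumptions. The coding also drops the restriction to COVID-19-related admissions and the Day 29 limit.

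**Working it through.** The SAP gives no figure to reproduce here, and no hospitalization or death rates. All event counts below are assumptions. Arm sizes of 100 and 122 are the planned sizes in SAP 5.2 for Arms 7-8 and Arms 9-11.

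**1. Text comparison**

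| Section | Event | Who is censored, as written |
|---|---|---|
| 6.10.3.1.6 | viral clearance | those without the event |
| 6.10.3.2.2 | symptom resolution | those without the event |
| 6.10.3.2.7 | symptom improvement | those without the event |
| 6.16.2.6 | hospital admission | those with the event |
| 6.16.2.8 | ICU admission | those admitted to the hospital or ICU |

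Only the last two rows are reversed.

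**2. Events available to the Cox model, 100 per arm (placebo/active)**

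| Assumed admission rates | Events as written | Events if those not admitted are censored |
|---|---|---|
| 3% / 1% | 0 / 0 | 3 / 1 |
| 7% / 2% | 0 / 0 | 7 / 2 |
| 10% / 3% | 0 / 0 | 10 / 3 |

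**3. Worked Cox example.** Assume 100 per arm, placebo admissions on Days 2, 3, 4, 5, 6 and 8, one active admission on Day 5, and everyone else censored at Day 29. With the rule corrected, the fitted hazard ratio is 0.163 (95% CI 0.020 to 1.352) on 7 events. Rough check: the ratio should be near 1/6 = 0.167, and the standard error of its logarithm near √(1/6 + 1/1) = 1.08. The interval is then about exp(ln 0.163 ± 1.96 × 1.08), or 0.020 to 1.35. As written there are 0 events and no fit.

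**4. Bayesian outcome: count.** Suppose 7 participants meet the composite and d of them die without admission. The model codes 7 − d as events: 7, 6, 5 or 4 for d = 0, 1, 2 or 3. The shortfall always equals d.

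**5. Bayesian outcome: effect on the posterior.** For each arm, logit(p_i) = α_i, with likelihood p_i^y (1 − p_i)^(n − y) and a normal prior centred at 0. The posterior is computed on a fine grid. The SAP states a prior for α_1 (placebo) only, so the active-arm prior is an assumption. The same standard deviation (SD) is used in both arms and varied. The quantity is P(active rate < placebo rate). One placebo event is taken to be a death without admission.

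| n per arm | Composite events, placebo vs active | Prior SD | Death counted | Death coded 0 | Change |
|---|---|---|---|---|---|
| 100 | 4 vs 1 | 100 | 0.939 | 0.877 | −0.062 |
| 100 | 4 vs 1 | 10 | 0.936 | 0.872 | −0.064 |
| 100 | 4 vs 1 | 2.5 | 0.902 | 0.823 | −0.079 |
| 122 | 4 vs 1 | 100 | 0.939 | 0.877 | −0.062 |
| 122 | 4 vs 1 | 10 | 0.936 | 0.872 | −0.064 |
| 122 | 4 vs 1 | 2.5 | 0.900 | 0.821 | −0.079 |
| 100 | 6 vs 1 | 100 | 0.986 | 0.970 | −0.016 |
| 100 | 6 vs 1 | 2.5 | 0.972 | 0.947 | −0.025 |

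Rough check for the diffuse prior: with rare events, equal arms and one active event, the probability is about 1 − (1/2)^y, where y is the placebo count. That gives 1 − 1/16 = 0.938 for y = 4 and 1 − 1/8 = 0.875 for y = 3. Arm size cancels, which is why the 100 and 122 rows barely differ.

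**The case against.** The case for leaving this alone is about weight, since the wording itself is not in dispute.

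- **The censoring slip is self-evident.** A Cox run with no events fails at once, so it cannot yield a misleading estimate; the realistic cost is a query to the statistician. This stands for 6.16.2.6. It does not cover 6.16.2.8, where supplying the 'not' still leaves ward-only patients undefined and someone would have to choose a rule.
- **Never-admitted patients are not wholly without limits.** The endpoint is evaluated only in the treatment and assessment period, whose end is defined in SAP 6.1.3. That bounds their follow-up, but the explicit censoring instruction remains wrong.
- **The ICU error has little effect.** No model or test is planned, and a summary of admitted patients needs no censoring. This stands: only the optional graph could be affected.
- **The Bayesian outcome may be shorthand.** The heading and the parent section define the composite, and a programmer might carry it over. But the coded definition is explicit and excludes death if followed. It matters only if someone dies without a qualifying admission.
- **The sizes are illustrative.** This is true: counts and the active-arm prior are assumed, and the section states no decision threshold, so no changed conclusion is shown.
- **The two errors are unrelated.** This is fair, and neither adds weight to the other.

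**Conclusion.** Both errors are real, and the severity is minor.

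The censoring rule in 6.16.2.6 is reversed and, followed literally, leaves the planned Cox model with no events whatever the admission rates. That a 'not' was dropped is an inference, strongly supported by the event definition and the three parallel rules. In 6.16.2.8 the same sentence conflicts with its section, but the descriptive summary can still be produced. Both sections fall under the heading "Additional Exploratory Analyses Not Defined in the Protocol", and admissions are still reported through the proportions in 6.16.2.9, the composite in 6.10.3.3.1 and the listings.

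The Bayesian model checks a different outcome from the composite by exactly the number of deaths without admission. With one such death in the assumed examples, the posterior probability of benefit falls by 0.016 to 0.079, depending on event counts and prior. With none, the change is exactly zero. The primary endpoint and the frequentist composite analysis are unaffected.

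**What to change.** - **6.16.2.6:** state that a patient who has *not* been admitted to the hospital by completion or early discontinuation is censored at the last visit in the treatment and assessment period. Drop the reference to the ICU.
- **6.16.2.8:** state the same rule for a patient who has *not* been admitted to the ICU, naming the ICU only, so that ward-only patients are covered.
- **6.10.3.3.1.1:** define r_ij = 1 if participant j had a COVID-19-related hospitalization (using the eCRF definition in 6.10.3.3.1) or died from any cause by Day 29, and 0 otherwise. In the closing sentence, replace the deterioration label with the name of this endpoint.

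Neither time-to-event section says how a death before admission is handled; one sentence on that could go into the same edit.

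The cost is a few words in three sections and the matching programming. No new data or analyses are needed, and no primary or secondary frequentist result changes.
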